A Single Arm Phase II Pilot Study of Euthyroid Hypothyroxinemia in Metastatic Breast Carcinoma

*Principal Investigator: [name]

**Co-Investigators: [name]

Sponsor: Aultman Health Foundation

Protocol ID: 2018.08.ST

ClinicalTrials.gov Identifier: NCT03787303

Version: 5.0 [April 8, 2020]

*, ** This is the intellectual property of the above mentioned and may not be reproduced, used, claimed ownership, republished, reprinted, created and/or generated regarding its content without our written and legal consent.

1.0 Background and Rationale:

It is estimated that there are approximately 155,000 living with metastatic breast cancer in the US and the number is estimated to increase over the next years (SEER data). Although their median survival has improved over the last 2 decades from 17 months to approximately 24 months attributed to newer treatments, there is an ongoing need for additional strategies and research to improve survival and quality of life. (2,3,4)

Many studies have explored the connection between hypothyroidism and hyperthyroidism and breast cancer with varied results ranging up to one third prevalence. Low T3 and elevated TSH levels have been detected in newly diagnosed breast cancer patients. Other studies have suggested that some of the common symptoms reported by breast cancer survivors such as fatigue and depression can be attributed to subclinical hypothyroidism. (2,3,4)

L-thyroxine (T4) is the most commonly prescribed agent for the management of hypothyroidism in the US. However, there are data suggesting that T4 is a potent pro-oncogenic agent. Proposed mechanisms include stimulation of mitogenesis, angiogenesis and resistance to apoptosis, opposition of anti-PDL-1 and radiation effects. It has been postulated that the avbeta3integrin that is universally expressed on cancer cells harbors a thyroid hormone receptor and T4 interacts with it. (2,3,4)

Triiodothyronine (T3) on the other hand, is significantly less oncogenic and less mitogenic and is downstream of T4 which is a t3 pro-hormone. Therefore, exogenous supplementation of T3 would decrease the T4 levels creating the desired state of euthyroid hypothyroxinemia. (2,3,4)

Previous Data

Phase 2 clinical trial of recurrent GBM (Hercbergs et. al) demonstrated that this strategy was feasible and tolerable however due to small numbers and heavily pretreated population with high (expected) mortality, conclusive results are pending. (2,3)

Cross sectional retrospective compassionate use study inducing euthyroid hypothyroxinemia successfully reported improved progression free and overall survival in patients with high grade synovial sarcoma and brain stem glioma 8 and 7 years. (2,3)

Rationale and Hypothesis

The rationale of this study is to replace L-thyroxine (T4) with Triiodothyronine (T3) in hypothyroid patients with metastatic breast carcinoma while they continue to receive standard systemic therapy, titrating the dose to achieve a state of euthyroid hypothyroxinemia which in turn would result in a lower risk of disease progression and improved survival by lowering the concentration of T4.

2.0 Primary Objective

1. To prospectively evaluate the progression-free survival in hypothyroid patients with metastatic breast carcinoma who are rendered euthyroid and hypothyroxinemic.

Secondary Objectives

1. To quantitate the prevalence of hypothyroidism in metastatic breast cancer patients.
2. To monitor QOL at baseline, 3, 6, 9 and 12 months.
3. To prospectively study the feasibility and average time required to achieve the euthyroid hypothyroxinemia state in qualifying patients.

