4.0 Study Procedures

It is anticipated that 20% of the patients with metastatic breast cancer will qualify for participation in this study. Patients who screen fail after meeting initial eligibility will be asked to allow record follow-up so the data can be used for the initial endpoint of prevalence. Rescreening will not be permitted.

Following consent and confirmation of eligibility participants will have their L-thyroxine (T4) discontinued and Triiodothyronine (T3)/liothyronine sodium initiated at 3: 1 mcg respectively. Study will allow use of Triiodothyronine (cytomel/liothyronine) and all available generic liothyronine sodium compounds. Triiodothyronine dosing will be rounded up to the closest commercial dose available. For patients on L-thyroxine there will be a washout period of four (4) days between discontinuation and the initiation of triiodothyroinine. Day 0 will be the day of enrollment. Day 1, or day 5 (if washout required) will be the day of the first dose of Triiodothyronine treatment. Triiodothyronine tablets are administered orally as a once a day dosing, or split dosing at the Investigators discretion. Usual maintenance dose is 25 to 75mcg daily. It will be recommended that the drug be taken at the same time each day, but this is not mandatory.

Drug titration will be in accordance with thyroid function testing to maintain levels of free T4 at <50% normal range. The treatment period will continue for 9 months (270 days). In the event of loco/regional recurrence or progression there is no need to discontinue study treatment because this is not one of the endpoints.

During the treatment period participants will have lab testing every 4 weeks for the first 12 weeks and then every 12 weeks until study drug is discontinued. Participants will be scheduled for a clinic visit every 12 weeks. Compliance with Triiodothyronine (T3) and adverse events will be assessed at each clinic visit. Disease state will be assessed at 3, 6, 9, and 12 months via clinical examination, laboratory results and radiographic findings performed as part of routine care. Participants will also be asked to complete a Quality of Life survey (FACT-B) at each clinic visit.

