Unscheduled visits and management for metastatic breast cancer are at the discretion of the investigator. Unscheduled visits may include physical examinations, vital signs, ECOG performance status, concomitant medication, adverse event collection, disease symptoms assessment, laboratory testing, Triiodothyronine (T3) dose adjustments, or to resumed dosing, if previously interrupted.

Discontinuation of Study Treatment: At the end of the treatment period, the investigator will have the discretion to resume thyroxine or continue Triiodothyronine (T3); however, if it is not covered by insurance the patient will be responsible.

If subjects discontinue study treatment prematurely for any reason they will be asked to continue follow-up until study completion.

All patients will be scheduled for a 12-month safety follow-up visit.

TABLE 1: SCHEDULE OF STUDY PROCEDURES

Study Phase	Screening	Study Visits			Follow Up Visit
Visit		3mo (+/- 14 days)	6mo (+/- 14 days)	9mo (+/- 14 days)	12mo (+/- 14 days)
ECOG PS	X	X	X	X	X
Informed Consent	X				
Review Inclusion/Exclusion Criteria	X				
Demographics/Medical History	X				
Physical Examination	X	X	X	X	X
Vital Signs: BP, HR, RR	X	X	X	X	X
EKG	X				
Disease assessment	X	X	X	X	X
FACT-B QOL questionnaire	X	X	X	X	X
Prior/Concomitant Medications	X	X	X	X	X
Clinical Laboratory Evaluation*	X	X	X	X	X
Pregnancy Test (women of childbearing potential only)	X				
Adverse Event Assessment	X	X	X	X	X

- *TSH, FreeT3, FreeT4, CBC, CMP every 4 weeks for the first 12 weeks and then every 12 weeks until end of study.
- Additional lab work at physician's discretion.

Study Drug

Cytomel (liothyronine sodium) is a commercially available compound which is a synthetic formulation of triiodothyronine. Study drug may be obtained from the Aultman Hospital Retail Pharmacy or the pharmacy of the participant's choice. The cost will be charged to the participant/insurance company unless they meet the hospital's indigent policy, in which case study drug will be provided free of charge.

Cytomel capsules should not be opened, crushed, or chewed. Patients should store the Cytomel capsules in the original package provided and be instructed to keep all medication out of reach of children. Further details obtained from accessdata.fda.gov can be found in appendix D.

HOW SUPPLIED

Cytomel (liothyronine sodium) Tablets: 5 mcg in bottles of 100;

25 mcg in bottles of 100; and 50 mcg in bottles of 100.

5 mcg 100's: NDC 52604-3414-1

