7.0 Statistical Methods

Baseline Data

Baseline and demographic characteristics will be summarized by standard descriptive summaries (e.g., means and standard deviations for continuous variables such as age and percentages for categorical variables such as gender).

Analysis of Primary Outcome of Interest

The primary analysis will include all subjects meeting all inclusion and exclusion criteria and completing Visit 1.

The primary endpoint will be the progression free survival at 12 months

Secondary endpoints will include:

- the prevalence of hypothyroidism in successive metastatic breast cancer patients,
- the change in QOL measures between baseline, 3, 6, 9 and 12 months and
- the duration of time to achieve the euthyroid hypothyroxiemic state

Sample Size and Power

The sample size is estimated to be approximately 30 patients.

Given the many uncertainties to calculate power precisely, this is an estimate made, based on clinical experience.

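### Objective 3 names feasibility, but its only listed endpoint is a duration that exists only for patients who reach the target state; no endpoint counts how many do

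*Protocol*

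**What the plan says.** Section 2.0 of the protocol gives the third secondary objective as "To prospectively study the feasibility and average time required to achieve the euthyroid hypothyroxinemia state in qualifying patients". Feasibility and average time stand side by side, and the group is qualifying patients, not successful ones.

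Section 7.0 lists three secondary endpoints: prevalence of hypothyroidism, change in quality of life, and "the duration of time to achieve the euthyroid hypothyroxiemic state". Only the third serves objective 3. The section gives no proportion reaching the state, no time limit for success and no feasibility target.

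Other relevant text:
- Section 3.0 names an intent-to-treat population for analysis.
- Section 4.0 sets the laboratory target: "Drug titration will be in accordance with thyroid function testing to maintain levels of free T4 at <50% normal range". Treatment lasts 270 days. Panels are drawn every 4 weeks to week 12, then every 12 weeks.
- Section 4.0 foresees early stopping: "If subjects discontinue study treatment prematurely for any reason they will be asked to continue follow-up until study completion".
- Section 1.0 describes median survival in metastatic disease as having improved "from 17 months to approximately 24 months". Section 3.0 admits patients with an expected survival of more than 3 months.
- On size, section 7.0 says: "The sample size is estimated to be approximately 30 patients".

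**The concern.** A time to reach the state exists only for a patient who reaches it. Someone who dies or stops T3 beforehand, or is still off target at 9 months, contributes no value. Taken literally, the average describes achievers only, and the patients who show that the strategy did not work appear in no listed endpoint. The protocol's own survival figure and its provision for early stopping make such patients likely.

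The share reaching the state is what a pilot of this strategy most needs to report. The hypothesis in section 1.0 runs through lowering T4, and the primary objective concerns patients who have been brought into the state. If only half get there, that changes how progression-free survival is read and whether a larger trial makes sense. The endpoint list as written would not show it.

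**Working it through.** **Plan's own figure.** The sample size of about 30 cannot be reproduced, because section 7.0 gives no inputs: "Given the many uncertainties to calculate power precisely, this is an estimate made, based on clinical experience". The point does not depend on how that number was reached.

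**Step 1: can the endpoint tell success from failure?** Let k of 30 patients reach the state, with mean time 8 weeks among them (assumed). The literal average is (k × 8)/k = 8 weeks for every k. For contrast, count each non-achiever at week 36, the last on-treatment panel: (k × 8 + (30 − k) × 36)/30.

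| k of 30 | Literal average | Non-achievers at week 36 | Proportion, exact 95% CI |
|---|---|---|---|
| 30 | 8.0 weeks | 8.0 weeks | 100% (88% to 100%) |
| 24 | 8.0 weeks | (192 + 216)/30 = 13.6 weeks | 80% (61% to 92%) |
| 15 | 8.0 weeks | (120 + 540)/30 = 22.0 weeks | 50% (31% to 69%) |

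The 8 weeks is illustrative. The equality down the second column holds for any distribution of achiever times that is the same in each row.

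**Step 2: how much does selecting achievers shorten the time?** The protocol gives no attainment rate, so a range is assumed.
- Onset is exponential, with p attaining by week 12: hazard h = −ln(1 − p)/12.
- Death is exponential with a 24-month median (104.3 weeks). There are no other T3 stops.
- Panels fall at weeks 4, 8, 12, 24 and 36. A patient is an achiever if alive at the first panel at or after onset.
- The comparator is the mean onset in all patients restricted to 36 weeks, (1 − e^(−36h))/h, so that no credit or debit is taken beyond treatment. At p = 50%, h = 0.0578 and the result is 17.31 × (1 − 0.125) = 15.15 weeks.

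Simulation of 2,000,000 patients per row (times in weeks):

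| p by week 12 | Share achieving | Achievers, exact onset | All patients, restricted to 36 weeks | Shortening | Achievers, recorded panel date |
|---|---|---|---|---|---|
| 30% | 58% | 14.10 | 22.10 | 36% | 18.3 |
| 50% | 79% | 11.52 | 15.15 | 24% | 15.4 |
| 70% | 90% | 8.49 | 9.70 | 12% | 11.9 |
| 80% | 93% | 6.83 | 7.40 | 8% | 9.9 |
| 90% | 95% | 4.99 | 5.21 | 4% | 7.8 |

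**Step 3: what would the trial record?** It sees panel dates, not onset (last column). These run later than onset and offset the selection effect. Against the restricted mean, the recorded average is shorter at 30%, about equal at 50%, and longer at 70%, 80% and 90%. The selection effect is real, but the net direction of the recorded average is not fixed.

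**The case against.** The strongest reply has four parts.

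1. The protocol nowhere says that feasibility is measured by time. Objective 3 names two things, and the endpoint in section 7.0 is a duration with no mean and no restriction to achievers. A Kaplan-Meier or cumulative-incidence summary would fit that wording. This stands against any claim that the text scores feasibility by average time. It does not supply the missing count: feasibility is named and no endpoint measures it.

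2. Section 3.0 states intent to treat, and objective 3 refers to qualifying patients. So the protocol does not instruct anyone to drop non-achievers. That is right, but a population label does not give a duration to a patient who has none.

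3. Censoring, competing events and the choice of mean or median usually belong in a statistical analysis plan, which is not at hand. That also stands, and their absence is not the finding. The finding is the mismatch, within the protocol, between a feasibility objective stated with an average time and an endpoint list without a proportion.

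4. A reader might infer that the reported average will be too short. The documents do not support that. They give no attainment rate, and panel spacing lengthens recorded times enough to outweigh selection in three of the five scenarios above. An accidental offset of this kind does not repair the endpoint, but it rules out a claim about net direction.

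**Conclusion.** The point holds in limited form. Sections 2.0 and 7.0 read together leave feasibility without an endpoint that counts successes, and an average duration is undefined for patients who never reach the state. The literal average can therefore be identical at 50% and at 100% success. It need not be: the equality requires similar times among achievers in both cases. This conclusion rests on no assumed rate.

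The shortening from selection, about 36% down to 4% on exact onset, depends wholly on the assumed attainment rates, exponential onset and the 24-month survival figure. It is small if nearly everyone attains early. It describes one component and not the recorded average.

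The objective is secondary, in a small descriptive pilot with no feasibility threshold attached. The change is worth making because it is cheap, but it does not undermine the design.

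**What to change.** Amend sections 2.0 and 7.0.

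1. **Feasibility endpoint.** List the proportion of all patients who start the T4-to-T3 switch who reach the protocol-defined state by the end of treatment, with an exact 95% CI. A fixed earlier panel, such as week 12, can be added. Patients who die or stop T3 before reaching the state, or who never reach it, count as not achieving. Patients who reach it and later die or stop count as achieving.
2. **Time endpoint.** Replace average time with the cumulative incidence of first reaching the state in all such patients, with death and permanent T3 stop before attainment as competing events. Read the median from the curve if it is reached.

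Both need a written laboratory definition of the state that can be scored from the panels. Section 4.0 gives a free T4 titration target; the investigators should state what else, if anything, the definition requires.

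**Cost.** This is a protocol amendment to wording plus that definition. No new visits, patients or blood draws are needed, since TSH, free T3 and free T4 are already scheduled. The reported time may become longer, or the median may not be reached. The proportion will be imprecise at 30 patients: 24 of 30 gives 80%, with an exact interval of 61% to 92%.

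### Secondary objective 3 names feasibility and an average time to euthyroid hypothyroxinemia, but section 7.0 lists only the duration, which by itself would not show how many patients fail to reach the state

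*Protocol*

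**What the plan says.** Section 2.0 (Secondary Objectives, item 3) has two components: feasibility, and the "average time required to achieve the euthyroid hypothyroxinemia state in qualifying patients". Section 7.0 lists three secondary endpoints, and the only one that matches this objective is "the duration of time to achieve the euthyroid hypothyroxiemic state". No proportion reaching the state and no feasibility criterion appears there or elsewhere in the protocol.

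The laboratory target is in section 4.0: "Drug titration will be in accordance with thyroid function testing to maintain levels of free T4 at <50% normal range". The scheduled measurements are "lab testing every 4 weeks for the first 12 weeks and then every 12 weeks until study drug is discontinued". The footnote to Table 1 gives the same frequency and adds that further labs may be drawn at the physician's discretion. Treatment lasts 9 months (270 days). Patients who stop study treatment early are asked to remain in follow-up. Section 3.0 names an intent-to-treat population in general terms, without tying it to this endpoint.

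On size, section 7.0 says: "The sample size is estimated to be approximately 30 patients". No expected achievement rate or expected time to the state is given.

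**The concern.** The objective asks two questions: can the state be reached, and how long does it take? The endpoint list answers only the second. The one summary the protocol names for it, an average, has no value for a patient who never reaches the state. If the average is taken over the times that exist, it is conditioned on success.

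Failure to reach the state is a realistic outcome here. Patients have metastatic disease, the entry criterion asks only for a life expectancy above 3 months, and early stopping of T3 is foreseen. The proportion also matters beyond this objective. The primary objective concerns patients who have been brought into the state, so a progression-free survival result at 12 months is hard to interpret without knowing how many got there.

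**Working it through.** **Figure to reproduce.** None. The protocol states no rate, time or precision for this objective, and the sample size rests on clinical experience ("Given the many uncertainties to calculate power precisely, this is an estimate made, based on clinical experience").

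**Side by side.**

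| Component | Section 2.0, objective 3 | Section 7.0, endpoints |
|---|---|---|
| Feasibility | named | no endpoint |
| Time to the state | named, as an average | named, as a duration |

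**Illustration.** From the protocol: N = 30 and scheduled labs at weeks 4, 8 and 12, then every 12 weeks (weeks 24 and 36 within the 270 days). Assumed: k patients achieve, split equally over weeks 4, 8 and 12; the other 30 − k never achieve and are followed to week 36; there are no deaths or stops. Values of k from 6 to 30 are chosen to show the range.

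- Mean among achievers: (k/3)(4 + 8 + 12)/k = 24/3 = 8.0 weeks. The k cancels, so the failure count cannot enter.
- Proportion: k/30, with an exact (Clopper–Pearson) 95% interval.
- Median over all 30: the first lab week by which at least half have achieved. With no competing events in the illustration, cumulative incidence and one minus Kaplan–Meier coincide.
- Mean time restricted to 36 weeks over all 30: [8k + 36(30 − k)]/30. For k = 15 this is (120 + 540)/30 = 22.0.

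| k of 30 | Mean, achievers only (weeks) | Proportion (95% CI) | Median, all 30 (weeks) | 36-week restricted mean, all 30 (weeks) |
|---|---|---|---|---|
| 30 | 8.0 | 100% (88–100%) | 8 | 8.0 |
| 24 | 8.0 | 80% (61–92%) | 8 | 13.6 |
| 15 | 8.0 | 50% (31–69%) | 12 | 22.0 |
| 9 | 8.0 | 30% (15–49%) | not reached | 27.6 |
| 6 | 8.0 | 20% (8–39%) | not reached | 30.4 |

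The achievers' mean is the same in every row. The proportion separates the rows. The median does so only in part: it is 8 weeks at both 100% and 80%. This is why the proportion should be the main addition and the median a supplement.

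**Precision at N = 30.** 27/30 = 90% has an exact interval of 73–98%, and 15/30 = 50% has 31–69%. These do not overlap, so even this sample size tells a regimen that mostly works from one that works half the time.

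**A second assumed pattern.** Suppose the time to the state is exponential with mean 8 weeks among patients able to achieve it, with labs at weeks 4, 8, 12, 24 and 36. The probabilities of first being seen in the state at those labs are 0.393, 0.239, 0.145, 0.173 and 0.039 (sum 0.989). The mean recorded time is (4×0.393 + 8×0.239 + 12×0.145 + 24×0.173 + 36×0.039)/0.989 = 10.8/0.989 = 10.9 weeks. A fraction who never achieve multiplies every probability by the same factor, which cancels again. The invariance therefore does not depend on the equal split assumed above.

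**The case against.** The strongest case on the other side has four parts.

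1. The objective does name feasibility. A reader might infer that poor feasibility would be hidden in the trial's results. The protocol does not support that: a proportion could be reported under the objective as written. What stands is narrower. The endpoint list has no measure for it, and an analysis that followed section 7.0 literally would report durations only.

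2. No sentence excludes patients who do not reach the state. A reader might infer a planned achievers-only analysis, but the protocol prescribes none. The wording in section 7.0 is compatible with a time-to-event analysis, and estimator and censoring rules are commonly left to a statistical analysis plan, which is not at hand. This is largely right. However, section 2.0 itself names an average, and section 7.0 itself drops half of the objective. The general intent-to-treat sentence does not help, because a non-achiever in that population still has no time to average.

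3. A reader might infer that times after week 12 will be recorded up to 12 weeks late. That is a worst case. The lab schedule is a minimum, since extra labs and unscheduled visits are allowed, and limited resolution is inherent in any laboratory-defined endpoint. It is a caveat for reporting and not an error.

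4. This is the third secondary objective, with no threshold or decision attached, and every rate above is assumed. Both points are accepted, and they limit the severity. They do not affect the cancellation of k, which is structural.

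**Conclusion.** The point holds as a mismatch between sections 2.0 and 7.0, together with a poorly chosen summary. Feasibility is promised and has no endpoint. The one summary named, read as a plain average of observed times, is undefined for non-achievers and insensitive to how many there are: 8.0 weeks at 6/30 and at 30/30 under the assumed times. The listed endpoint alone would not show poor feasibility.

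The size of the effect in this trial cannot be stated, because the protocol gives no achievement rate or expected time. Severity is low to moderate.

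**What to change.** 1. Add to the endpoint list in section 7.0 the proportion of all patients starting T3 who reach the state by fixed scheduled lab times, for example week 12 and week 36, with an exact 95% confidence interval and non-achievers counted as failures.

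2. In section 2.0, replace the average with a cumulative incidence estimate of time to the state over all T3 starters. Treat death and stopping T3 as competing events, and censor patients still on T3 who have not achieved the state at their last lab. Use a cumulative incidence estimator, because standard Kaplan–Meier and Turnbull estimates do not handle competing events. Report the median if it is reached.

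3. State in the report that times are resolved only to the scheduled lab interval of 4 to 12 weeks unless extra labs were drawn.

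**Cost.** A wording change in two sections and slightly more analysis, using labs already scheduled. The feasibility figure may look less favourable than an average among achievers, and the median may not be reached.
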